Week 4 to Week 8 ensures that approximate steady-state conditions are reached prior to the pharmacokinetics phase. A schematic presentation of the study design is provided in [Figure 3-1](#).

[figure not shown]

The pharmacokinetics will be assessed for primary objectives during Week 8 to Week 12 at approximate steady-state conditions. The rationale for this is to avoid the expected larger inter-individual variation in exposure at treatment initiation due to the potentially different levels of target expression between patients. This would result in high variability in the pharmacokinetics parameter leading to an increased sample size of the study. Further, the approximate steady-state condition is a clinically relevant situation as full target depletion would be expected in contrast to the situation after administration of a single dose typically used for bioequivalence assessment. During the study, ofatumumab will be administered to the respective groups of patients by a health care provider and according to specified instructions.

No clinically significant difference in ofatumumab exposure is expected between the two administration sites (abdomen vs thigh) ([Xu et al 2010](#)). Groups 3 and 4 will enable an assessment of the pharmacokinetics of ofatumumab injected to the thigh which can then be compared to abdominal administration using the PFS and AI, respectively. The aim of assessment of the injection site influence on ofatumumab pharmacokinetics is not to demonstrate bioequivalence but to enable an evaluation of the potential clinical significance of differences in pharmacokinetic parameters. Potentially, the absorption rate may vary between different injection sites for subcutaneous single dose administration of ofatumumab possibly resulting in different Tmax and Cmax values. However, under steady-state conditions and with the primary target being depletion of CD20-positive B-cells, the comparison of AUCs over the dosing period would be the most relevant parameter to evaluate. In order for patients to obtain a clinical benefit from participation in the study, continued treatment with ofatumumab will be offered to the eligible patients through enrollment into the umbrella open-label Phase 3 extension study (COMB157G2399). Patients waiting for open label extension study to open can continue to receive study drug. Patients should return every 12 weeks and complete assessments per [Table 6.1](#).

Part 3 – Safety follow-up/Extension study

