5.5.4 Instructions for prescribing and taking study treatment

The study medication (ofatumumab injections) will be dispensed starting at the Randomization Visit (Day 1). Drug will then be dispensed at planned visits throughout the treatment period according to [Table 6-1](#). On Day 7 and Day 14, the same time-window (+/- 1 day) as for study visit applies. Starting at Week 4, the subcutaneous injections should be administered at 4-Week (28 days) intervals (+/- 3 days).

All investigational drugs will be administered at site by a HCP/study nurse. The study medication will be administered as subcutaneous injections either to the abdomen or to the thigh depending on the randomization. For each of the two injection areas, study medication should be administered in an alternating fashion in accordance with the graphics in [Figure 5-1](#) Alternation of injection areas for abdomen and thigh.

In order to assess tolerability of the initial dose of study medication patients will be closely monitored following administration for any reactions including injection related. Patients must remain at the site under observation for a minimum of approximately **5 hours** following dosing on Day 1. Vital signs should be obtained 30-60 minute before sc injection (if premedication is administered, pre-injection vital signs should be obtained before premedication is administered), and again approximately 60 min post-injection on Day 1, 7, 14 and Week 4 and 8.

Figure 5-1 Alteration of injection areas for abdomen and thigh

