Table 6-1 lists all of the assessments and indicates with an “x” when the visits are performed. Subjects must be seen for all visits on the designated day, or as close to it as possible. Missed or rescheduled visits should not lead to automatic discontinuation. In case a visit is performed outside the schedule, subsequent visits shall be performed in keeping with the original visit schedule. In addition to the scheduled visits, patients may have unplanned visits due to a MS relapse, an acute illness of undetermined cause, for other reasons, or at the discretion of the Investigator. Data collected during unplanned visits will be recorded in the unplanned visit CRFs. Patients who prematurely discontinue the study for any reason should be scheduled for a visit as soon as possible, at which time all of the assessments listed for the final visit will be performed. At this final visit, all dispensed investigational product should be reconciled and the adverse event and concomitant medications reconciled on the CRF.

Table 6-1 **Assessment schedule**

Period	Screening/Pretreatment		Induction					Pharmacokinetics							
	SCR D-30 to D-8	BL D-7 to D1	D1 ¹	D4	D7	D14	W4 D28	W6 D42	W8 D56	W8 D57	W8 D59	W9 D63	W10 D70	W11 D77	EOS ² / W12 D84
Visit															
Visit No.	1	20	110	120	130	140	150	160	170	180	190	200	210	220	1999
Visit Window (hours or days)	n.a.	n.a.	n.a.	±1d	±1d	±1d	±1d	±3d	±1d	±1d	±1d	±2d	±2d	±2d	±2d
HIV test	X														
eCSSRS	X ^{9a}	X ^{9a}	X	X	X	X	X	X	X	X	X	X	X	X	X
AEs	X	X	X	X	X	X	X	X	X	X	X	X	X	X	X
Prior/Con Meds ¹²	X	X	X	X	X	X	X	X	X	X	X	X	X	X	X
Study Disposition															X

1. Randomization and first dose (usually expected on the same day). If first dose occurs on a different day after randomization, the day of first dose should be considered to be Day 1. Patients must remain at the site under observation for a minimum of 5 hours following dosing on Day 1.
2. EOS visit will be required for all patients (Patients who permanently discontinue study drug and patients who complete the study). Patients waiting for open label extension study to open can continue to receive study drug. Patients should return every 12 Weeks and complete all EOS assessments with the exception of PK, [REDACTED] and ECG.

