3. Syphilis and Tuberculosis testing must be done as part of eligibility check (Exclusion criterion #10) unless completed in the last 6 months prior to screening with documented negative results. For tuberculosis testing, QuantiFERON®-TB Gold test can be done by the local lab to assess patient's eligibility at Screening.
4. For the first injection (Day 1), the addition of premedication with steroids (methylprednisolone 100 mg iv. or equivalent) is recommended. Premedication with acetaminophen and/or antihistamines (or equivalent) is recommended and may be administered at the discretion of the Investigator. Premedication should be administered 30 to 60 min prior to study drug injection.
5. Vital signs should be obtained 30-60 min before sc injection (if premedication is administered, pre-injection vital signs should be obtained before premedication is administered), and again approximately 60 min post-injection on Day 1, 7, 14 and Week 4 and 8.
6. A complete physical examination will be performed at the visits indicated in [Table 6-1](#) and will include an assessment of skin, head and neck, lymph nodes, heart, lungs, abdomen, back, neurological function and comments on general appearance. A complete neurological examination will be part of the initial physical examination at Screening.

7. Pregnancy test is conducted on female patients only: Serum pregnancy tests will be conducted at Screening and EOS visit. Urine pregnancy tests will be conducted at all other scheduled visits as indicated in [Table 6-1](#) prior to dosing. The results will be captured in source documents.
8. Patient's contraception status must be reviewed and documented in source to ensure method of contraception continues to be appropriate per protocol requirement for highly effective contraception.
9. a) Assessment can be conducted either at Screening OR Baseline visit. b) Assessment can be conducted at either the Baseline OR the Day 1 visit (they must be conducted before the first dose of investigational treatment. Labs must be drawn to allow adequate time for results to be obtained before randomization to ensure patient's eligibility)
10. On non-injection visits the PK (Plasma) [REDACTED] samples can be drawn at any time during the visit.
[REDACTED]
[REDACTED]
12. Including corticosteroids used to treat MS relapse.
13. Labs must be drawn to allow adequate time for results to be obtained before randomization to ensure patient's eligibility.

[REDACTED]

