Table 6-2 Assessment schedule for Safety Follow-up period

Visit Week ¹ (relative to EOS)	+W12	+W24	+W36	Every 12 Weeks ²	End of Safety-FU ³
Visit Number	410	420	430	440/4XX	2999
Visit window (days)	±14	±14	±14	±14	
AEs	X	X	X	X	X
Concomitant Meds*	X	X	X	X	X
Vital Signs	X	X	X	X	X
eCSSRS	X	X	X	X	X
Urine pregnancy test ⁴	X	X	X	X	X
Contraception status	X	X	X	X	X
Sample for Total IgG, IgM	X	X	X	X	X
Routine Labs	X	X	X	X	X
Follow up Disposition					X

W=week.

1. Time measured from the EOS visit
2. As needed for the patients requiring [REDACTED] (Section 3.1)
3. If planned visit and End of Safety-FU occur at the same time only End of Safety-FU visit should be done. If patient is prematurely withdrawn from the Safety-FU period, the End of Safety-FU assessments should be done at the time of withdrawal
4. Female patients only: monthly urine home pregnancy testing will be conducted between clinic visits. The patient must contact the Investigator immediately in the case of a positive test for confirmatory testing at the Investigator's discretion

* including steroids for MS relapse and newly started disease modifying therapy as applicable

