6.6.4 Laboratory evaluations

A central laboratory will be used for analysis of all specimens collected. Details on the collections, shipment of samples and reporting of results by the central laboratory are provided to Investigators in the laboratory manual. Abnormal laboratory parameters, inconsistent with clinical presentation of MS or which cause suspicion of an underlying medical condition, should be repeated for confirmation.

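### Patients kept on study drug while waiting for the extension have two of every three doses without a planned visit or a scheduled pregnancy test

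*Protocol*

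**What the plan says.** **Waiting period.** Protocol 3.1, repeated in SAP 1.1, states: "Patients waiting for open label extension study to open can continue to receive study drug. Patients should return every 12 weeks". Table 6-1 footnote 2 gives the content of these visits: "Patients should return every 12 Weeks and complete all EOS assessments with the exception of PK". ECG and a redacted item are also left out. The last visit column of Table 6-1 is EOS/Week 12.

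**Dosing.** Section 5.5.4 states: "All investigational drugs will be administered at site by a HCP/study nurse". It also states: "Starting at Week 4, the subcutaneous injections should be administered at 4-Week (28 days) intervals". No end is given for that interval. The same section ties dispensing to the planned visits of Table 6-1, and 5.5.2 has each medication number correspond to an arm and to a particular visit. Sections 6.7.2 and 9.3 plan a dose at Week 12.

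**Pregnancy testing.** Table 6-1 footnote 7 states: "Serum pregnancy tests will be conducted at Screening and EOS visit. Urine pregnancy tests will be conducted at all other scheduled visits". It places the urine tests before dosing, and 6.6.6 gives the same split between serum and urine. Section 6.6.4 says of laboratory work in general: "A central laboratory will be used for analysis of all specimens collected". Section 5.6.2 lists pregnancy among the reasons for permanent discontinuation. For female patients in safety follow-up, Table 6-2 footnote 4 states: "monthly urine home pregnancy testing will be conducted between clinic visits".

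**The concern.** Up to Week 8 the plan joins three things: the dose, a planned visit, and a urine pregnancy test before the injection. For patients who wait for the extension this link breaks. Doses continue every 4 weeks, but the only visits described come every 12 weeks. The doses in between have no column in Table 6-1, no visit to which a pack can be linked, and no list of assessments.

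The pregnancy stopping rule is where this matters most. It can act before a dose only if a result is at hand, and for the in-between doses no test is scheduled. Between clinic visits, the documents schedule more pregnancy testing for women who have stopped drug than for women still receiving it, and they give no reason.

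There is also a smaller cost to the data. Safety, including injection-related reactions, is a secondary objective, and SAP 2.8.1.1.1 reports reactions by injection number with an open-ended sequence. Waiting-period injections can enter those summaries without a defined visit at which the information is collected.

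**Working it through.** This is a count of schedules; no error-rate or sample-size formula applies.

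**1. Reproduce the plan's own count.** Section 9.3 expects 6 injections. Days 1, 7, 14, 28, 56 and 84 give 6, so the Week 12 (Day 84) dose is planned and falls on the EOS visit.

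**2. Overlay the two schedules after Week 12.** Dose interval 28 days (5.5.4); visit interval 12 × 7 = 84 days (3.1 and footnote 2). Doses per visit interval: 84 / 28 = 3.

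| Dose | Planned visit | Scheduled pregnancy test | Age of last scheduled test sample |
|---|---|---|---|
| Week 12 | EOS | Serum, same visit | Same day |
| Week 16 | None | None | 4 weeks |
| Week 20 | None | None | 8 weeks |
| Week 24 | 12-weekly EOS panel | Serum, same visit | Same day |

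The pattern repeats: Weeks 28 and 32, then 40 and 44, have no planned visit. From Week 12 up to but not including Week 24, 36 or 48, the share is 2/3, 4/6 and 6/9, which is 67% each time. Counting only doses after Week 12, a wait that ends just after Week 16 gives 1 of 1, just after Week 20 gives 2 of 2, and just after Week 24 gives 2 of 3.

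**3. Gap between scheduled tests.** Planned dosing visits before EOS are at most 28 days apart (Day 28 to Day 56). In the waiting period the gap between scheduled tests is 84 days. This takes footnote 7 at its word that pre-dose urine tests apply at the earlier dosing visits; the pregnancy row of Table 6-1 is missing from the text available for review.

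**4. Illustration.** Suppose conception occurs just after the Week 12 sample. The doses at Weeks 16 and 20 both precede the next scheduled sample, at Week 24. If the Week 24 serum result is known before that day's dose, 2 doses are given before any scheduled test could show the pregnancy. If it is not, the number is 3. Turnaround time is not stated, so the range is 2 to 3.

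**5. Week 12 and each later 12-weekly dose.** The scheduled test is serum, and footnotes 9 and 13 of Table 6-1 require time for laboratory results only before randomization. No sentence says whether a pregnancy result must be in hand before the Week 12 or any later dose.

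**The case against.** The strongest reply is that nothing here is impossible. A patient can attend every 28 days for the injection and complete the EOS panel every 12 weeks. That stands. A reader might infer that the sections cannot all be followed, or that dosing would drift to 12-week intervals. The documents do not support this: 5.5.4 fixes the 4-week interval and 5.5.5 does not permit dose adjustments or interruptions. The fault is that the in-between attendances are undefined.

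A reader might also infer that these doses carry no safety checks at all. That goes too far. Section 7.1 requires questioning about adverse events at each visit, 7.7 requires the suicidality scale at each visit including unplanned ones, and Section 6 provides unplanned-visit forms. If sites log the attendances as unplanned visits, those checks apply. Pregnancy testing has no equivalent, because footnote 7 and 6.6.6 tie it to scheduled or planned visits.

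It is tempting to say that the Week 12 dose is given before the serum result is known. The text does not show that. The central-laboratory sentence in 6.6.4 is general and has exceptions: dipstick urine goes to the central laboratory only if abnormal, and the tuberculosis test may be run locally. The visit windows (2 days at EOS, 3 days for dosing) do not force dosing before a result. A late result is possible, not established.

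Two further points limit the size. Women of child-bearing potential must use highly effective contraception, reviewed at visits (4.2, 6.6.6). Section 3.6 describes the extension as following directly, so few patients, or none, may wait. Finally, the dispensing sentence in 5.5.4 speaks of the treatment period. If that ends at Week 12, waiting-period doses have no dispensing rule, which leaves the gap open.

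**Conclusion.** The point holds in a limited form. For patients who stay on drug while waiting for the extension, two of every three doses over each full 12-week cycle have no planned visit and no scheduled pregnancy test. This follows from the text and needs no assumption about laboratory turnaround. It does assume that the 28-day interval, stated without an end, continues to apply after Week 12. Separately, the protocol does not say how the EOS serum result relates to the dose given at that visit.

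The number of patients affected cannot be given. The visit gap reaches only those who wait, and neither their number nor the length of the wait is stated. A reader might take the approximately 150 randomized patients as the number at risk at Week 12. That is the wrong denominator for the pregnancy point, which concerns only women of child-bearing potential.

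The Week 8 to Week 12 endpoints, the power and the bioequivalence test are unaffected. This is a gap in safety conduct that is worth closing because it bears on a mandatory stopping rule and costs little to correct.

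**What to change.** Reconcile Protocol 3.1 and Table 6-1 footnote 2 with 5.5.2, 5.5.4, Table 6-1 footnote 7, 6.6.6 and 6.7.2, so that:

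- each dose from Week 12 on, including every waiting-period dose, belongs to a defined contact in Table 6-1, with its assessments listed;
- the protocol states how the pregnancy stopping rule in 5.6.2 operates for those doses, including how the EOS serum result relates to a dose given at the same visit.

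The choice of test, its timing and the rule itself are for the sponsor. SAP 1.1 repeats the waiting-period text and should be brought into line.

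The cost is protocol wording, made through a written amendment under 11.1, and a few assessments. No additional attendance is created, because 5.5.4 already brings the patient to the site for each injection.

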3.2 Rationale for study design

The study is a parallel-group design with four groups (PFS (abdomen), AI (abdomen), PFS (thigh), and AI (thigh)). The two main groups are designed to address the primary objective of demonstrating bioequivalence. The two additional groups are designed to address the secondary objective of evaluating potential difference in the pharmacokinetic parameters with different administration sites. The parallel-groups design is chosen to avoid potential carryover treatment effect which is difficult to control with a cross-over study design. The primary and secondary objective will be evaluated during approximate pharmacokinetic steady-state conditions anticipated during Week 8 and Week 12. This will contribute to a reduction of variability between subjects compared to an assessment after a single dose. Further, an evaluation at steady-state will be more clinically relevant.

3.3 Rationale for dose/regimen, route of administration and duration of treatment

The dosing regimen for ofatumumab in this study comprises an initial induction phase with 20 mg subcutaneous administration on treatment initiation (Day 1) and on Day 7, and Day 14. Thereafter, the maintenance regimen will be subcutaneous administration of 20 mg every 4 weeks starting at week 4. Subcutaneous injection is the route of administration used in the Phase 3 program.

The duration of the study is planned to be 12 weeks.

3.4 Rationale for choice of comparator

There is no comparator in this study.

3.5 Purpose and timing of interim analyses/design adaptations

An interim analysis of the variability of Cmax and AUCtau is planned to enable a re-estimation and potential increase of the final sample size in case the observed variability is higher than initially predicted. This interim analysis is to be conducted when approximately 36 patients total completed Week 12 in the PFS (abdomen) and AI (abdomen) treatment groups.

3.6 Risks and benefits

The risk to subjects in this trial will be minimized by compliance with eligibility criteria, close clinical monitoring, avoidance of prohibited treatments and adherence to protocol contraception requirements and Investigator guidance regarding specific safety areas.

Ofatumumab is approved for treatment of CLL and is administered via iv infusion at doses up to 2000 mg. Risks in this population include: infusion reactions, tumor lysis syndrome, cytopenia, progressive multifocal leukoencephalopathy (PML), hepatitis B virus (HBV) infection and reactivation, and bowel obstruction (please refer to locally available Arzerra® Prescribing Information). The dose of ofatumumab in this study in MS patients is 20 mg; ie, 100 times lower than the dose used in CLL. 267 RRMS patients have been exposed to

ofatumumab (i.v. N=38 and sc N=229 in 2 Phase 2 studies (Study OMS115102 and OMS112831). No unexpected safety findings were observed in MS patients who received ofatumumab in the completed studies. In the 48-week, placebo-controlled, cross-over study (cross-over at 24 weeks) of iv. doses of ofatumumab up to 700 mg (OMS115102), adverse events reported more frequently on ofatumumab vs placebo included: rash, throat irritation, erythema, fatigue, viral infection and flushing. In the placebo-controlled, dose-ranging study of ofatumumab (OMS112831) administered at sc doses up to 60 mg every 4 weeks for up to 24 weeks, injection-related reactions were observed more frequently in the overall ofatumumab group. Safety and tolerability of ofatumumab is currently being further investigated in two large global Phase 3 studies (COMB157G2301 and G2302), with a planned total sample size of 1800 randomized patients. A DMC is monitoring the safety and risk/benefit for the Ofatumumab controlled, blinded studies

Ofatumumab sc has demonstrated profound suppression of MRI lesion activity ($\geq 90\%$ versus placebo over Weeks 4-12) in relapsing MS patients in the Phase 2 studies. Confirmation of clinical efficacy will be evaluated in the Phase 3 studies (Study COMB157G2301 and G2302). The efficacy of ocrelizumab, another intravenously administered B-cell depleting compound on clinical and MRI disease activity has been reported in 2 Phase 3 trials in relapsing MS patients ([Hauser et al 2017](#)). Taken together, available information of relevant clinical and MRI outcome supports the potential efficacy of ofatumumab in patients with relapsing MS.

The OMB157G2102 study involves dosing for 12 weeks which is a short treatment period for MS patients. Therefore, in order to provide a clinical benefit and balance the potential risks associated with B cell depletion, all patients eligible will be offered enrollment in the umbrella open-label extension trial (OMB157G2399) in direct continuation of the G2102 study.

Overall, the balance of benefit and risk supports the rationale of COMB157G2102 study to evaluate the bioequivalence, pharmacokinetics, and immunogenicity in combination with additional safety and efficacy data obtained from the open-label extension study (G2399) of ofatumumab sc to address the unmet medical need of patients with RMS.

4 Population

The study population will consist of adult patients with RMS fulfilling all the eligibility criteria listed below. The study is planned to be conducted in approximately 30 centers worldwide. It is aimed to randomize a total of 150 patients. To reach this number it is anticipated that the total number of patients to be screened is approximately 200 depending on the screen failure rate. Patients, who have been randomized and prematurely discontinue study, will not be replaced. In the event that sample size is to be increased after the planned interim analysis, the number of sites and patients to be screened may be increased to accommodate the increase of up to 284 total randomized patients.

